Prospective, randomised controlled trial assessing MedCu copper dressing for lower limb ulcer management

(CUPRA trial, Copper dressings for Ulcers; Prospective Randomised Appraisal)

Version 1.0, dd 18 October 2024

Chief Investigator's Statement of Ownership and Content.

I, [name], confirm that this protocol is my work and is owned by me. The protocol conforms with standards outlined in the Declaration of Helsinki 1964.

Name (PRINT):____[name]______

Signature:_______

Date: _________

RESEARCH PROTOCOL SUMMARY

| TITLE: | Prospective, randomised controlled trial assessing MedCu copper dressing for lower limb management | | | |
|----------------------|---|--|--|--|
| | (CUPRA trial, Copper dressings for lower limb Ulcers; Prospective Randomised Appraisal) | | | |
| Short title: | CUPRA trial | | | |
| IRAS ethics number | 350241 | | | |
| ISRCTN trial number | To be confirmed | | | |
| Device description | CE-marked wound dressing: MedCu (by MedCu Technologies) dressings are impregnated with copper oxide microparticles. MedCu dressings are single-use wound dressing with an internal absorbent layer and one or two external non-woven, non-adherent layers. | | | |
| Study design | Prospective, randomised controlled trial | | | |
| Primary objective | To determine the relative efficacy and safety of MedCu copper-impregnated dressing versus standard of care for the management of lower limb ulcers, measured through wound status (healed vs non-healed) at 12 weeks post-baseline. | | | |
| Secondary objectives | To determine the wider efficacy and safety of MedCu copper- impregnated dressing for the management of lower limb ulcers at 4, 8 and 12 weeks post-baseline - Any adverse events related to the use of allocated dressings, and rates of (patient-requested) discontinuation of dressing Wound status (healed vs non-healed) - Quality of Life (EQ-5D-5L) - Lower limb symptoms (VEINES Sym) - Types of dressings applied in standard care arm | | | |
| Patient population | First known randomised controlled trial of MedCu dressing. Therefore pragmatic approach to allow inclusion of wider cohort of patients. Patients with lower limb ulcer of any underlying aetiology are considered for inclusion. Index wound size should be minimum of 1cm² and can be maximum of 30cm² (only one index wound per patient to be included in study). Stratification for wound size at randomisation stage. | | | |

| | Participants must not be palliative and have the mental and physical capacity to provide informed written consent and complete patient reported outcome measures. Participants are recruited from the local hospital / community clinics. |
|--------------------|---|
| Sample size | The primary outcome, wound status (healed vs non-healed) is used for sample size calculation. Treatment will be random and 1:1 allocation: n = 33 standard of care and n = 33 MedCu copper dressing cases, giving a combined total of n = 66 participants. |
| | The sample size calculation is based on 2x2 Chi-squared test (80% power and 5% alpha). The hypothesis is a minimum 20% (effect size 0.40) difference in wound healed at week 12, with then allocation for 30% withdrawal/dropout rate added. |
| | Option to expand sample size, subject to review of safety data, after initial sample size has been reached. This then allows wound healing comparison for purer sample of 'leg ulcers' and 'foot ulcers' separately from each other. For each of these subsamples, 66 participants are to be recruited. |
| Sponsor | North Cumbria Integrated Care NHS Foundation Trust |
| Funder | Creed Health [name] [contact] Email: [contact] E: [contact] W: https://www.creedhealth.co.uk/ |
| Chief Investigator | [name], vascular specialist nurse, Vascular Surgery Dept, North Cumbria University Hospitals NHS Trust, Cumberland Infirmary, [name] [contact] |
| Co-investigators | [name] PhD, Research Project Lead, [contact]; Cumbria Partnership NHS Foundation Trust R&D Department, Cumberland Infirmary, [name] [contact] |
| | [name], Head of Podiatry, North Cumbria Integrated Care NHS Foundation Trust, Cumberland Infirmary, [name], [contact] |

| Organisations where research will take place | North Cumbria Integrated Care NHS Foundation Trust Cumberland Infirmary, [name] | | | |
|--|--|--|--|--|
| | Optional: up to 2 other NHS Trusts, exact sites to be determined (once trial has been listed on National Institute for Health Research National Portfolio) – amendment to be | | | |
| | submitted to HRA once additional site identified. | | | |
| Planned timeline | First patient, first visit: 1Mar2025, | | | |
| | Last patient, first visit: 31Apr2026 | | | |
| | Last patient, last visit: 30Jul2026 | | | |
| | Trial end date: 30Sep2026 | | | |

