4.5 Outcome measures

4.5.1 Primary outcome measures

Wound status (healed vs non-healed)

In line with the definition used by the VenUS6 research trial team, the primary outcome of this trial is time to healing of the reference ulcer, and the definition is: complete epithelial cover in the absence of a scab (eschar) with no dressing required. There is no minimum length of time that the index site has to have been in said condition for when participant present for follow-up study visit.

4.5.2 **Secondary outcome measures**

Clinical outcome measures

- ulcer size, measured digitally with Healthy io App
- Size and characteristics of ulcer, determined with PUSH score
- Quality of life score, determined with EQ-5D-5L score.
- Patient discomfort related to legs, VEINES Sym questionnaire

- Patient withdrawal rates due to change in management (e.g. need for surgery)
- Lower limb ulcer infection rates
- Types of dressing used in the standard care arm (non-antimicrobial and antimicrobial)

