5. SUBJECTS

5.1 Anticipated number of research subjects

Below a summary is given for the sample size needed. The primary outcome, wound status (healed vs non-healed) is used for sample size calculation for both randomisation groups.

The sample size calculation has been performed using GPower freeware sample size calculator, based on 2x2 Chi-squared test for wound healed status. Power calculation for sample size assumes 80% power and 5% two-sided confidence interval.

Table 4: standard care vs MedCu dressing. The hypothesis is that MedCu dressing performs better to a minimum 20% (effect size 0.41) in wound healed at week 12.

Since some patients may withdraw over the course of the 12-week trial period, a 20% dropout rate is calculated into each sample size. A 1:1 allocation to the two types of dressing is applied.

Note: There will be an option to expand sample size, subject to no safety concerns after initial sample size has been reached. This then allows wound healing comparison for purer sample of 'leg ulcers' and 'foot ulcers' separately from each other. For this purpose, the same effect size will be applied. The hypothesis is that MedCu dressing performs better to a minimum 20% (effect size 0.40), requiring a sample size 66 (taking into account same 30% drop-out/withdrawal rate)

Table 4, Sample size calculations

| | Sample size calculation | | | | | |
|------------------|---|---|--|--|--|--|
| | Standard care control dressing | Intervention dressing (MedCu copper dressing) | | | | |
| Ulcer healed | 40% | 60% | | | | |
| Ulcer not healed | 60% 40% | | | | | |
| | Power beta of 80%, Alpha p-value of 0.05, effect size 0.40 Sample size required without any drop-out: 50 patients Sample size with 30% attrition rate included: 66 patients Total of 66 patients, distributed as: - 33 Patients to receive MedCu dressing - 33 Patients to receive standard care dressing | | | | | |

The CONSORT guidelines require a statement on the number of patients assessed for eligibility (Schulz, Altman & Moher 2010). The number of patients screened but who did not meet the inclusion criteria or who declined to participate will be recorded, as will any patients who are lost to follow-up (Appendix 5).

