9.3 Medical Device management and use of different compression bandage brands

MedCu dressings will be stored in the NHS store and clinic rooms at the temperature recommended by the respective manufacturers. No requirement for involvement pharmacy or clinical trials pharmacist. Standard approved and available stocks of dressings and compression bandaging to be used for any standard care activities.

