APPENDIX 1. INTERVENTION DEVIATION AND LOWER LIMB ULCER INFECTION

There may be incidences where a participant may either:

- Develop a reaction to the allocated dressing.
- Becomes completely non-compliant (possibly due to allocated dressing being uncomfortable, or eg hospital admission)
- Improve to such an extent that allocated dressing is no longer indicated.

In such instances the patient and/or clinician can opt to stop or pause treatment with the dressing in question. If this occurs, this needs to be recorded (date and reason), and the decision can then be made to either:

- Discontinuation of intended dressing due to improvement in symptoms (including wound healed). Participant will still continue to be assessed as per planned dates and timepoints.
- Change over to an alternative dressing that is not the originally allocated type. This is allowed but only if there are clinical indications to do so or at patient request if they cannot tolerate the allocated dressing. Patient can later in trial period be transferred back to original allocated bandage type if required.
- Pausing or discontinuation of wound dressing when not clinically indicated. Even if lower limb ulcer persists and patient no longer wears allocated dressing, they can still continue in the trial if they wish. Outcome measures will continue to be recorded as per planned dates and time points.
- Pause or discontinuation due to adverse event. Patient can remain in trial provided they are capable to continue with follow-up schedule and completion of outcome measures. If not possible, see next point regarding 'Withdraw patient from study'.
- Withdraw patient from study.
 - o At the request of the patient
 - For clinical reasons, eg if the leg ulcer has deteriorated to such an extent that emergency surgical or medical intervention is required which means return to use of any dressing in reasonable time frame (within time to next trial follow-up visit) is not feasible. In this case, this needs to be reported as a (Serious) Adverse Event if discontinuation is due to deterioration of the index wound or index leg only.

When overall trial participation for a patient is finished early, the participant will still be asked to complete the relevant questionnaires (provided they have capacity to do so):

- Week 4, week 8 and week 12 VEINES Sym questionnaire
- Week 12 EQ5D5L QoL questionnaire

Infection and use of antibiotics during trial

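### The dressing-discontinuation rate leaves out clinician-led stops for intolerance and has no event definition that means the same thing in both arms

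*Protocol*

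**What the plan says.** The Research Protocol Summary, under secondary objectives, pairs dressing-related adverse events with "rates of (patient-requested) discontinuation of dressing". Neither section 3.2 nor section 4.5.2 repeats this rate. Section 4.5.2 lists withdrawals caused by a change in management, which is a different event.

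On the arms, section 5.1 states "A 1:1 allocation to the two types of dressing is applied". One type is a single manufacturer's copper dressing. The other is a class: section 4.5.2 makes an outcome of "Types of dressing used in the standard care arm (non-antimicrobial and antimicrobial" products, and section 9.3 says "Standard approved and available stocks of dressings and compression bandaging to be used for any standard care activities".

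On stopping, Appendix 1 covers a reaction to the allocated dressing, non-compliance and improvement, and says "In such instances the patient and/or clinician can opt to stop or pause treatment with the dressing in question", with date and reason recorded. One of the listed courses is "Change over to an alternative dressing that is not the originally allocated type", permitted "only if there are clinical indications to do so or at patient request if they cannot tolerate the allocated dressing". The paragraph on infection in the same appendix classes a clinician's decision to stop the allocated dressing as an intervention deviation.

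Section 7.1 collects the specific dressing used, and Table 3 records dressing use status at weeks 0, 4, 8 and 12. Neither asks why a product was changed.

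**The concern.** There are two separate problems.

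1. **Completeness.** The rate is limited to stops that the patient asks for. A stop that a clinician makes because of a reaction is at least as informative about tolerability, and it is left out.
2. **Comparability.** If the event is leaving the allocated type, it means giving up one product line in the MedCu arm and giving up a whole formulary in the standard-care arm. The same intolerance, handled in the ordinary way, can produce an event in one arm and none in the other.

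The rate is one of the two safety measures named together in the summary's objectives. The option to expand the sample depends on a review of safety data (summary) and on there being no safety concerns (section 5.1), and section 8 says that no trial steering committee will be convened. An incomplete or lopsided tolerability figure could therefore bear on a real decision. It also cannot be put right at the analysis stage if the reasons for product changes in standard care were never collected.

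**Working it through.** The protocol gives no expected discontinuation rate, margin or test for this outcome, so there is no figure of its own to reproduce. The check is a reading of the text followed by an illustration.

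**Reading the text**

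- *Who can stop.* Appendix 1: "the patient and/or clinician can opt to stop or pause treatment with the dressing in question". The summary counts patient-requested stops only. Clinician-led stops are therefore recorded but not in the rate. This limit is the same for both arms.
- *What counts as leaving.* Allocation is to two types (section 5.1), and the change-over course in Appendix 1 refers to a dressing outside the allocated type. Read together, moving from one standard product to another stays inside the allocation, and any move off copper leaves it.
- *What is recorded.* Date and reason are required for Appendix 1 events. Nothing clearly requires them for a swap between two standard products.

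**Illustration**

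The only input from the protocol is 33 patients per arm (summary and Table 4). The rest are assumptions:

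- p = true probability of product intolerance, equal in both arms
- q = share of resulting stops that the patient requests, equal in both arms
- s = share of standard-care intolerances solved by a swap inside the arm, and so not counted

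Counted rate, MedCu = p × q. Counted rate, standard care = p × q × (1 − s). The ratio is 1/(1 − s), in which p and q cancel.

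| p | q | s | MedCu, expected of 33 | Standard care, expected of 33 | Ratio |
|---|---|---|---|---|---|
| 0.10 | 1 | 0.5 | 3.3 (10%) | 1.7 (5%) | 2 |
| 0.10 | 1 | 0.8 | 3.3 (10%) | 0.7 (2%) | 5 |
| 0.20 | 1 | 0 | 6.6 (20%) | 6.6 (20%) | 1 |
| 0.20 | 1 | 0.5 | 6.6 (20%) | 3.3 (10%) | 2 |
| 0.20 | 1 | 0.8 | 6.6 (20%) | 1.3 (4%) | 5 |
| 0.20 | 0.5 | 0.5 | 3.3 (10%) | 1.7 (5%) | 2 |
| 0.30 | 1 | 0.5 | 9.9 (30%) | 5.0 (15%) | 2 |

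Three things follow.

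1. The imbalance comes from s alone.
2. The patient-requested limit (q) lowers both rates and leaves the ratio unchanged. From q = 1 to q = 0.5 at p = 0.20 and s = 0.5, the gap falls from 10 to 5 percentage points.
3. If within-arm changes for intolerance are counted too (s = 0), the ratio returns to 1.

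For scale, two-sided Fisher exact p-values at 33 per arm are: 3 v 0, 0.24; 5 v 0, 0.053; 7 v 0, 0.011; 7 v 1, 0.054; 7 v 3, 0.30.

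**The case against.** The strongest reply is that the asymmetry is inferred. No section defines discontinuation, and none says that a swap between standard products goes uncounted. The word type is used at arm level in section 5.1 but at product level in the summary and section 4.5.2. Appendix 1 also speaks of the dressing in question, which could mean the product in use, so that a standard-care patient who reacts to it would be recorded. That is a fair reading. It shows that the event is ambiguous, and it leaves the rate without a fixed meaning. Counting rules can be left to an analysis plan, but the reasons for product changes have to be collected during the trial.

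Some stronger readings are tempting and should be resisted.

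- *The patient-requested limit makes the arms non-comparable.* It applies to both arms, so by itself it only under-counts. It would bias the comparison only if the split between patient-led and clinician-led stops differed by arm. That is possible because participants know their dressing, but nothing in the protocol shows it.
- *Clinician-led stops are lost.* They are recorded with date and reason, classed as deviations, and a reaction can also appear among dressing-related adverse events.
- *A significant false difference is to be expected.* A split of 7 v 0 (p = 0.011) needs every MedCu stop to be patient-requested and every standard-care intolerance to be solved by a swap. At 7 v 3 the p-value is 0.30. Section 7.3 names no test for this rate.
- *Every product change should count.* This could tilt the rate the other way. A move from a non-antimicrobial to an antimicrobial product because of infection says more about the wound's course than about tolerability.

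It is also fair to say that freedom to change product is part of a pragmatic standard-care comparator. That supports allowing the change. It does not support leaving its reason unrecorded when a tolerability rate is to be reported.

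**Conclusion.** The concern holds in limited form. As worded in the summary, the rate omits clinician-initiated stops for a reaction and so under-counts intolerance in both arms; this follows directly from the text. Discontinuation is also undefined, and on the most natural reading of Appendix 1 the event is easier to trigger on MedCu than on standard care. At equal tolerability the rate would probably run against MedCu, by a factor of 2 if half of standard-care intolerances are solved within the arm and 5 if 80% are. Those shares are assumptions. The direction depends on the arm-level reading of type, which the protocol implies but does not state.

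This is a secondary outcome named only in the summary, and the week-12 healing result is unaffected. It should still be corrected before recruitment, because missing reasons cannot be recovered afterwards.

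**What to change.** Replace the summary's wording with one event that reads the same in both arms: the first change, pause or stop of the dressing product in use because of reaction, discomfort or intolerance, whether initiated by patient or clinician. Report patient-initiated and clinician-initiated events separately.

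- Exclude stops for healing or improvement, and routine formulary changes.
- Tabulate changes for infection or deterioration separately, outside the tolerability rate.
- Require date and reason for every product change in the standard-care arm as well. The product itself is already captured under section 7.1 and Table 3.
- Enter the outcome in sections 3.2 and 4.5.2 so that they agree with the summary, and keep it distinct from the withdrawal rate already listed in 4.5.2.

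The cost is protocol wording plus one reason-and-date field, with a little more recording for the nurses who change dressings. They will need a short reason code to separate intolerance from routine changes. None of this alters which dressings may be used or when they may be changed.

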1. LAY SUMMARY

Prompt appropriate treatment to heal lower limb ulcers is desirable to reduce the risk of complications (infection or even amputation) and to minimise the considerable costs involved in caring for chronic wounds. To date, clinicians have usually been guided by clinical signs (presence of redness, puss, bad odour) to determine if a wound is infected and may need antimicrobial dressings applied. However, there is limited evidence whether proactive antimicrobial dressing treatment may minimise the risk of wounds becoming infected, and if this approach may help accelerate wound healing. This present study will aim to determine if treatment of lower limb ulcers with a copper-oxide particle impregnated dressing (called MedCu, or 'copper dressing') can aid in wound healing of lower limb ulcers compared to standard care dressings. Copper is a known antimicrobial agent and there is early evidence that in parallel it can also help to accelerate wound healing. A minimum total of 66 patients with a lower limb (leg / foot) ulcer will be enrolled in this study, and allocated 1:1 to either standard care or the copper dressing. After a treatment period of up to 12 weeks, wound healing in the two groups will be compared to see if healing rates differ.

2. INTRODUCTION

Health and financial burden of ulcers

Chronic ulcers are associated with considerable expense, morbidity and impaired quality of life (Graves et al, 2022; Guest et al, 2020). The natural history and pathophysiology of lower extremity (foot and leg) wounds – particularly in those patients who have venous insufficiency and or other chronic disease affecting the vasculature such as diabetes and peripheral arterial disease - is a continuous cycle of healing and breakdown over years and sometimes decades (Raffetto et al, 2020). A positive relationship has been observed between eg venous leg ulcer occurrence and specific modern lifestyle risk factors such as sedentary lifestyles and obesity (Brand *et al* 1998). Bacterial infection of wounds carries the risk of further degenerative complications including cellulitis, necrotising fasciitis, and sepsis Grothier & Stephenson, 2015). It has long been recognised that an additional undesirable effect of wound infection is that it delays, or even stops altogether, the wound healing process (Raffetto et al, 2020, Halbert et al, 1992).

Copper and wounds

There is evidence that copper has unique properties in relation to wounds. It has been shown to 1) promote angiogenesis and 2) exert antimicrobial effects. In relation to the first point, various wound healing and repair mechanisms interplay with copper (Kornblatt et al, 2016).

Copper can stimulate angiogenesis, the formation of new blood vessels, by inducing generation of growth factors such as VEGF during the initial inflammatory response in a wound, and it also promotes subsequent cell migration and production of 'scaffolding' proteins such as collagens and elastin fibres in the proliferation and remodelling phases of wound healing (Gerard et al, 2010; Sen et al, 2002). This positive copper-derived effect on

wound healing has been demonstrated in wound animal models, and conversely copper inhibition delays wound closure (Kumar et al, 2020).

The antimicrobial effect of copper has been recognised and utilised for centuries. More recent research has elucidated in more detail the efficacy and mechanism of action for copper's antimicrobial activity against microorganisms (including bacteria). Though it can negatively impact microorganisms in different ways, the route of bactericidal activity is the the generation of reactive oxygen species, which irreversibly damages membranes and leads to breakdown of bacterial proteins, lipids and DNA (Salah et al , 2021; Borkow & Gabbay, 2005). Copper oxide impregnated wound dressings, possess potent antimicrobial properties. MedCu is one manufacturer of such dressings, and the devices have regulatory approval in place in a number of regions (USA, EU, UK) for use in treatment of acute and chronic wounds, such as diabetic ulcers, pressure injuries, and venous ulcers. These single use sterile wound dressings incorporate a highly absorbent layer and one or two nonbinding layers. All layers are impregnated with copper oxide microparticles, allowing continuous slow release of copper ions at very low concentrations (Borkow et al, 2022).

Real-world application of MedCu copper dressing

Initial findings of the efficacy of MedCu copper oxide dressings have been publish in recent years. One paper outlined the case of a hard-to-heal diabetic foot ulcer (DFU) and how MedCu dressing reduced the bioburden in the wound, as measured by fluorescence imaging, before wound closure was achieved (Lu et al, 2022). In a case series of four patients with mainly amputation-related wounds, uneventful healing was observed when MedCu dressing was applied (Melamed and Borkow, 2023). Unlike silver dressing, which should not be applied continuously for more than a few weeks, in these cases the MedCu copper dressing could be and were applied throughout. Wound healing, including that of lower limb ulcers, was also achieved in a large portion of patients when initial silver dressing was replaced with MedCu copper dressing (Gorel et al, 2024). Limitations of that study were the wider variation in wound aetiologies and the single arm approach without comparison to either standard care, continuation of silver dressing, or initial copper-based dressing treatment followed by silver. Similar results were obtained in a 13-patient cohort of diabetic foot ulcer patients (Melamed et al, 2021).

With this study, a real-world approach is taken to assess if MedCu copper dressing can aid in promoting wound healing when compared to standard of care. This also presents an opportunity to appraise the safety profile of copper dressing for use on lower limb ulcers.

